3.9.1 Other Secondary Outcomes

In addition to those parameters described in Section 3.6 above, the following will be summarized by treatment group as described:

• Vital Signs: blood pressure, pulse, body temperature, respiratory rate, oxygen saturation – summarized daily by treatment group

• Current symptoms –

Two analyses will be performed to compare the number of symptoms across groups:

- 1. The first analysis of symptoms will compute the average number of symptoms per day during the first 28 days for each patient as well as the average number of days with symptoms. Days with no information on symptoms, including days following the death or discharge of a patient, will be excluded. The groups will be compared using the Wilcoxon rank-sum test. An additional analysis will be conducted using the van Elteren stratified Wilcoxon test on the four strata defined by location (USA/Liberia/Sierra Leone versus Guinea) and cycle threshold (≤22 versus >22).
- The second analysis of symptoms will be identical to the above analysis, but only during the first 3 days. The rationale is that analyses over the entire 28-day period may be difficult to interpret because some patients will be discharged and others may die. Furthermore, the proportion discharged and proportion dying may differ by arm. Restricting attention to the first 3 days will focus the analysis on the initial stage which is free from discharges and some of the deaths.
 - Percent with any symptom
 - Daily summary of number of reported symptoms
 - Summarized for 7 day intervals by treatment group
 - Symptoms at day 28 and day 58 are also summarized.
- Chemistries: measurement of serum creatinine and potassium were required and will be summarized for each 3-day window (i.e. days 1- 3, days 4 6, etc.) by treatment groups, all other chemistries were considered optional and will be summarized as available
 - Additional subgroup analysis will repeat the above for adults and children
 - PCR: blood (note- any CT 40.0 or greater will be treated as negative)
 - \circ summarized for each 3-day window (i.e. days 1- 3, days 4 6, etc.)
 - if more than one PCR is available in a 3 day period for a given subject, the mean result will be used.
 - o summarized as change from baseline for each 3-day window
 - Both of the above will be presented as quantitative (continuous) and qualitative
 - Improvement or worsening of the CT value within the first 72 hours
 - Figure: Kaplan-Meier plot of time to negative Ebola PCR
 - Kaplan-Meier plot repeated for adults and children
 - Individual PCR curves will be presented
- PCR urine (as available)
 - \circ summarized for each 3-day window (i.e. days 1- 3, days 4 6, etc.) by treatment groups
 - presented as % positive
 - additional separate tables for adults and children
- Hematology, chemistries, and coagulation: optional data summarized as available
 - \circ summarized for each 3-day window (i.e. days 1- 3, days 4 6, etc.)
 - summarized as change from baseline for each 3-day window
 - additional separate tables for adults and children

- Urinalysis: optional data summarized as available
- Imaging and resuscitation: optional data summarized as available

32.1.1

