The day when the subject is enrolled and randomized to their assigned treatment arm is denoted as Study Day 0. The first day after randomization is Study Day 1. Subsequent days will be numbered chronologically through Day 58 of study. For each investigational agent being evaluated a unique schedule of assessments will be developed. The schedule of assessments will be harmonized across comparisons to provide the longitudinal data collection. Patients who agree to extended follow-up past Day 58 to determine the incidence of potential virologic relapse will either be seen in person or contacted via phone on a periodic basis; all study days past Day 58 will be considered Extended Follow-Up assessments. If necessary, and with the patient's verbal consent at the time they agree to extended follow-up, available medical staff and/or records at nearby treatment facilities may be consulted to determine whether the patient has recently been seen for any illnesses potentially consistent with a late onset virologic relapse syndrome. The expected frequency of such periodic assessments will be every 1-3 months up to one full year past Day 58, subject to the patients' wishes and the logistics and feasibility of contacting individual participants on a serial basis.

Table 9: Schedule of Evaluations

Evaluation / Procedure	Screen	Baseline	Follow Up										
Day +/- Window	-1 to 0	0	1	2	3	4	5	6	7	8+ while hospitalized	28- 35	58 ±7	Ext. F/U (Q 1-3 mo.)
ELIGIBILTY/RANDOMIZATION													
Informed consent	Х												
Demographics	Х												
Ebola PCR	-10 to 0												
Randomize subject		Х											
STUDY DRUG ADMINISTRATION	T	r					1		-				
ZMapp™ (if randomized to receive ZMapp™)		X (Day 0 if po	ssible)			ys from dose			ys from dose				
Investigational agents #2		Other in	vestiga	tional a	gents p	er the recent		e trial d	design,	refer to most			
MINIMUM STUDY PROCEDURES (only obtained	while in ti	reatment ur	nit)										
Vital signs		Х	Х	Х	Х	Х	Х	Х	Х	Х	Х	Х	
Record of Optimized Supportive Care		Х	Х	Х	Х	Х	Х	Х	Х	Х			
Assessment of current symptoms/conditions		Х	Х	Х	Х	Х	Х	Х	Х	Х	Х	Х	Х
Ebola PCR with ct		х		x				ry 2-3 days until 1 negative					
Creatinine, Potassium		Х		Х			Х		Х				
OPTIMAL STUDY PROCEDURES (In addition to the	he above.	May include	e any c	or all oj	f the b	elow)	-	-	-				
CBC with differential		Х	Х	Х	Х	Х	Х	Х	Х	Daily	Х	Х	
Ebola PCR with ct		Х	Х	Х	Х	Х	Х	Х	Х	until 2 negative	Х	Х	
Metabolic Panel		Х	Х	Х	Х	Х	Х	Х	Х	Daily	Х	Х	

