21.4.1 Baseline Evaluation

Within 24 hours prior to randomization, a baseline clinical evaluation will be performed with documentation of current symptoms and clinical conditions including vital signs.

The list of symptoms and signs to assess includes: fever, sore throat, cough, fatigue, weakness, dizziness, confusion, hearing loss, headache, myalgia, arthralgia, loss of appetite, vomiting, diarrhea, symptoms, abdominal pain, trouble urinating, chest pain, breathing difficulties, shortness of breath, hiccups, rash, edema, conjunctivitis, oral ulcers/thrush, hemorrhage, multi-organ failure, convulsions.

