3.4 Baseline Characteristics

The following baseline data will be summarized overall and by treatment assignment, geographic location (United States, Liberia, Sierra Leone and Guinea) and treatment center:

- Demographics: Age, sex, race, country of birth, work involving contact with a person with Ebola or decedents (N and %), and role (e.g., doctor, nurse, ambulance driver, laboratory) and enrollment in any other studies related to Ebola
- Clinical information: Results of pregnancy test, weight, height, blood pressure, pulse, body temperature, respiratory rate and oxygen saturation
- Illness information: days since onset of symptoms, cycle threshold (actual value and dichotomized as CT > 22 vs. CT ≤ 22), country where EVD diagnosis was confirmed
- Symptoms: Fever, sore throat, cough, etc.
- Chemistries: measurement of serum creatinine and potassium were required, all other chemistries were considered optional. Optional data will be summarized for subjects where data is available.
- Hematology and Coagulation: optional data summarized as provided.
- Urinalysis: optional data, summarized for subjects where data is available.
- Imaging and Resuscitation: optional data, summarized for subjects where data is available.

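### Both symptom tests leave out the required baseline symptom count; adjusting for it is a free but minor gain in power

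*Combined protocol and SAP*

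**What the plan says.** In the Final DAP, section 3.9.1 (Current symptoms), the first analysis will "compute the average number of symptoms per day during the first 28 days for each patient", together with an average number of days with symptoms. Then: "The groups will be compared using the Wilcoxon rank-sum test". On missing days: "Days with no information on symptoms, including days following the death or discharge of a patient, will be excluded". The only covariate control is a supplementary test: "An additional analysis will be conducted using the van Elteren stratified Wilcoxon test on the four strata defined by location" and cycle threshold (22 or below versus above 22). The shorter window uses the same methods: "The second analysis of symptoms will be identical to the above analysis, but only during the first 3 days".

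The amended protocol collects the same variable before treatment. Section 21.4.1 says that, within 24 hours before randomisation, "a baseline clinical evaluation will be performed with documentation of current symptoms and clinical conditions including vital signs", and it gives a fixed list of symptoms and signs. In the Schedule of Evaluations (section 21), the row "Assessment of current symptoms/conditions" is marked at Baseline among the minimum procedures, so it is not an optional item.

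The Final DAP uses baseline symptoms in two other places. Section 3.4 tabulates them ("Symptoms: Fever, sore throat, cough, etc"), and section 3.8 lists type of symptoms as a candidate predictor in the mortality risk score. Within 3.9.1, blood PCR and the optional laboratory data are summarised as change from baseline. The tested symptom outcome is not.

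**The concern.** A patient's symptom count shortly after randomisation is likely to be related to the count at entry. Where it is, part of the spread in the outcome can be predicted from data already collected. A test that ignores this treats that part as noise. With 72 patients randomised, and with section 3.9 itself acknowledging limited power, unused prognostic information matters more than it would in a large trial.

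The 3-day analysis is where this applies most naturally. It was added because the initial stage is free of discharges and of some deaths, and it is also the window closest to the baseline assessment. At stake are the precision of a lower-ranked secondary comparison and how it is read if the arms happen to differ in symptoms at entry.

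**Working it through.** **Is there a figure to reproduce?** No. The documents give no power, SD, effect size or baseline-to-follow-up correlation (rho) for the symptom tests. The size below is therefore a range over assumed values.

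**Inputs from the documents.** 72 randomised (Final DAP, section 2) at 1:1, so about 36 per arm. Tests as in 3.9.1. No alpha is stated for these tests. I take two-sided 0.05, in line with the one-sided 0.025 that section 3.8 gives for the supportive Barnard test.

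**Assumptions.** A true shift of 0.5 SD, a roughly normal baseline and outcome, and rho from 0 to 0.7.

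**Why adjustment helps.** Adjusting for a covariate with correlation rho multiplies the residual variance by 1 - rho². At rho 0.3, 0.5 and 0.7 this is 1 - 0.09 = 0.91, 1 - 0.25 = 0.75 and 1 - 0.49 = 0.51.

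**Simulated power, 36 per arm, 0.5 SD, two-sided 0.05.** The adjusted tests regress the rank of the outcome on the rank of the baseline count and compare arms.

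| rho | Planned Wilcoxon | Rank ANCOVA, ranks over all patients | Rank ANCOVA, re-ranked within the four strata |
|---|---|---|---|
| 0 | 52-53% | 52% | 49% |
| 0.2 | 52-53% | 53% | 49% |
| 0.3 | 52-53% | 56% | 52% |
| 0.4 | 52-53% | 58-59% | 54% |
| 0.5 | 52-53% | 63% | 58% |
| 0.6 | 52-53% | 69% | 65% |
| 0.7 | 52-53% | 79% | 73% |

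The third column is 3 to 6 points above the fourth. Re-ranking inside small strata therefore costs power, and at rho 0.3 or below it removes the gain altogether.

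I checked the recommended form itself, with ranks over all patients and CT and location added as covariates. The check used 6,000 runs and assumed about a quarter of patients in the smaller location, a CT split near 58/42, and a correlation of 0.4 between CT and baseline count. Power was 52%, 54%, 54%, 59%, 62%, 70% and 77% at the same rho values, within about 2 points of the third column. Size under the null was 5.1% at rho 0 and 4.8% at rho 0.6.

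**A larger effect.** With a shift of 0.66 SD (80% power for an unadjusted normal-theory test), the Wilcoxon has 76-77% at every rho. Rank ANCOVA has 76%, 80%, 86% and 95% at rho 0, 0.3, 0.5 and 0.7.

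**Chance imbalance.** One standard error of the baseline difference is sqrt(2/36) = 0.24 SD. A difference of that size moves the unadjusted comparison by rho × 0.24 SD, which is 0.07, 0.12 and 0.16 SD at rho 0.3, 0.5 and 0.7. Over all randomisations, the Wilcoxon's type I error is 4.7-4.9%. Among only those trials with a baseline difference above one standard error, it is 5.9%, 8.9% and 12.0% at those rho values. The adjusted test stays at 4.6-5.0%.

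**The case against.** The strongest reply is that the plan contains no error. An unadjusted Wilcoxon test in a randomised trial is valid, and chance imbalance is already part of its 5% error rate. That stands. A reader might infer from the omission that the symptom comparison is biased or its p-value invalid. The documents do not support this: the higher rates above hold only given that a sizeable imbalance has occurred.

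The second reply is that the gain depends on a correlation nobody has stated. That also stands. A reader might infer that baseline explains most of the variation in the 3-day outcome, but nothing in the documents shows it, and even rho 0.7 would explain only 49%. At rho 0.2 to 0.3 the gain is only about 1 to 3 points, and the 28-day average probably has a lower correlation than the 3-day one.

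Third, part of the issue is handled elsewhere. Baseline symptoms will be tabulated by arm, so an imbalance will be visible. The van Elteren test controls CT and location, which may capture some baseline severity. This reduces the point without removing it, because neither measure brings the symptom count into the comparison.

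Fourth, this outcome ranks below viral clearance and discharge, and section 3.9 warns that secondary results will be hard to read without a mortality benefit. The averages also drop days after death or discharge, which baseline adjustment does not address. Both statements are right, and they are why the point is minor.

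**Conclusion.** The point holds as a minor, free improvement in efficiency. Both symptom tests leave out a pre-randomisation measurement of the same variable that the schedule requires. Using it would raise power from about 52-53% by an amount between nothing (rho 0) and about 26 points (rho 0.7), with about 10 points at rho 0.5. It would also correct a chance difference in entry symptoms.

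The omission is certain from the text. Its size is not: it rests on 36 per arm, a 0.5 SD effect, two-sided 0.05, approximate normality and an assumed rho. It also rests on the baseline item having been completed, and section 3.5 only plans to report how complete it was. Nothing here affects the primary conclusion.

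**What to change.** Amend Final DAP 3.9.1 before unblinding:

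- For both windows, rank the average symptoms per day and the baseline symptom count over all patients. Compare arms by rank ANCOVA with baseline rank, CT stratum and location stratum as covariates. Do not re-rank within strata.
- State that the Day 0 assessment is the baseline and is not part of the outcome window. Section 3.9.1 does not say whether Day 0 counts among the first 28 or first 3 days; if it does, the outcome contains the baseline-day assessment.
- Keep the planned Wilcoxon and van Elteren tests as supportive analyses.

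The cost is two or three sentences and a few lines of code, with no new data. At rho 0 the check gave 52% against 53-54% for the Wilcoxon, so the price of adjusting for an uninformative baseline is at most one or two points. If treatment codes have already been opened, label the adjusted analysis post hoc. How to handle days after death or discharge remains a separate question.

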21.5.3.2 Optimal Daily Laboratory Monitoring

Refer to Schedule of Evaluations (Table 9) in Section 21.2. Testing should be performed during hospitalization and thereafter additionally as clinically indicated:

- CBC with differential
- Chemistry panels as available via POC testing, as defined in Section 6.3.2
- Ebola PCR with threshold cycle (ct)
 - After two negative Ebola PCRs, testing may be discontinued.
 - · Consideration of other bodily fluid sampling as clinically appropriate
 - Date of first PCR negative result
- PT / aPTT / INR
- D-Dimer
- Urinalysis, if available as POC test
- Specimen Storage

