On January 8, 2016, a provisional draft of the updated data analysis plan was shared with the Food and Drug Administration, Mapp Biopharmaceutical, INSERM, and other participating site investigators. The final data analysis plan detailed in the present document considers the comments that were received concerning that January 8th proposal. The document retains some of the information from the original analysis plan concerning the format and content of open and closed DSMB reports.

As of January 14, 2016, 42 days after the last case of EVD in Liberia was discharged, all three countries in West Africa had been declared Ebola-free. Accordingly, the study was planned for closure to new accrual as of that date. Subsequent to that determination there has been a potential resurgence of EVD reported in Sierra Leone; the scope and duration of that recent outbreak, as well as whether any potential new cases may be referred for enrollment, are unclear at this time. If additional enrollments do occur, this will delay the timeline for implementing the final study analysis as summarized in this document. As of the original

planned date of closure on 1-14-2016 there have been a total of 72 patients randomized on the protocol.

3 PLANNED Analyses

Unless otherwise stated, all tables, figures, and listings will show results by randomized arms. For tables with categorical variables, the number (%) will be presented. For tables with continuous variables, the mean, standard deviation, median, 25th and 75th percentiles, min and max will be presented. The number with missing values will also be shown. In calculation of percentages, subjects with missing data will not be included in the denominator. Data presented as listings or figures will be specifically noted.

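### From about day 7 the 3-day blood-PCR tables cover mainly patients not yet, or only just, cleared, so they overstate the percent still positive in both arms

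*Combined protocol and SAP*

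**What the plan says.** **Testing schedule (protocol Section 21, Table 9).** Under the minimum procedures, Ebola PCR is repeated every "2-3 days until 1 negative". Under the optimal procedures it is daily "until 2 negative", with further PCRs marked at Day 28-35 and Day 58. Section 21.5.3.2 adds: "After two negative Ebola PCRs, testing may be discontinued".

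**Missing results (Final DAP Section 3, Planned Analyses).** Categorical variables are shown as number and percent. "The number with missing values will also be shown". "In calculation of percentages, subjects with missing data will not be included in the denominator".

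**Blood PCR (Final DAP Section 3.9.1).** Results are summarised for each 3-day window, and again as change from baseline. "Both of the above will be presented as quantitative (continuous) and qualitative". Two rules govern the values: "any CT 40.0 or greater will be treated as negative", and "if more than one PCR is available in a 3 day period for a given subject, the mean result will be used".

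The Final DAP has no rule that carries a negative forward, fixes a denominator for these windows, or handles death or discharge in them. It does not say what CT a negative reported without a number contributes to a mean.

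**The concern.** Testing may stop because the patient has cleared virus. The general missing-data rule then treats that patient like one whose sample was never taken, and removes the patient from the percentage. What remains in a late window is patients not yet negative, plus those giving their first or second negative.

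A reader will take the percent positive at days 10-12 as the share of patients still viraemic. It is the share among patients whose testing had not already ended in success. The loss depends on the outcome being displayed, and it is heavier in whichever arm clears faster.

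The protocol lists comparative viral load kinetics as a secondary objective (Section 17) and change in threshold cycle per day as a secondary endpoint (Section 18.2.2). The Final DAP specifies no slope analysis, so these windows are its main group-level CT summary beyond 72 hours.

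**Working it through.** **1. The plan's own figure.** Final DAP Section 3.9 reports that 13 of 49 clearance times exceed 10 days: 13/49 = 26.5%, reproduced. So 49 - 13 = 36 patients, 36/49 = 73%, were negative by day 10 and could have stopped testing or be close to stopping.

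**2. Arithmetic on that figure, days 11-12.** Suppose only the 13 are still tested and k of them clear in the window (k is assumed).

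| k | Positive among the 13 | Positive among all 49 |
|---|---|---|
| 3 | 10/13 = 77% | 10/49 = 20% |
| 5 | 8/13 = 62% | 8/49 = 16% |
| 8 | 5/13 = 38% | 5/49 = 10% |

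This is the extreme case, since some patients would still be giving a second negative.

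**3. By arm, under assumed clearance times.** The documents give no clearance times by arm. Assume lognormal times in survivors, with medians 6.5 days (ZMapp) and 8.5 days (oSOC) and log-SD 0.45. The share not cleared by day t is 1 - Φ(ln(t/median)/0.45).

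- Calibration at t = 10: ZMapp 1 - Φ(0.957) = 0.169; oSOC 1 - Φ(0.361) = 0.359; average 0.264, against the documented 0.265.
- At t = 12: ZMapp 1 - Φ(1.362) = 0.087; oSOC 1 - Φ(0.766) = 0.222. Hence about 9% v 22% of survivors are positive at the end of the window.
- Counting patients not yet shown negative under testing every 3 days gives 12% v 29%.

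All deaths occurred within 8 days (Final DAP Section 3.8), so a survivor model suits days 10-12. Simulating 200,000 survivors per arm, scored by the last result in the window (ZMapp v oSOC):

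| Testing pattern | Shown, days 10-12 | Ratio | Difference |
|---|---|---|---|
| Daily until two negatives | 27% v 40% | 0.68 | 13 points |
| Every 3 days until one negative | 38% v 52% | 0.73 | 14 points |
| Random half of days, until two negatives | 19% v 35% | 0.54 | 16 points |
| All survivors | 9% v 22%, or 12% v 29% | 0.41 in both | 13 or 17 points |

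The third pattern is there because the Final DAP says that on many days half or fewer of participants were sampled.

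**4. Different assumptions.** Gamma times (shape 3 or 6), ZMapp/oSOC time ratio 0.75 or 0.60, scaled so that 26.5% clear after day 10. At days 10-12 the tested-only percent positive is 11-58% (ZMapp) and 37-73% (oSOC), against 2-14% and 22-37% of all survivors. Positivity is overstated from day 7 in every scenario. The ratio moves toward 1 in every one (days 10-12: 0.26-0.83 shown, 0.08-0.47 for all survivors). The point difference is equal or smaller at days 4-9, mixed at days 10-12 and larger from day 13. For example, with shape 3, ratio 0.75 and testing every 3 days, days 13-15 show 39% v 53% (14 points) against 5% v 15% (10 points).

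**5. The mean-result rule.** A CT of 38 (illustrative) and a negative at 40 average (38 + 40)/2 = 39. Being below 40, that counts as positive although the patient has cleared. Applied literally to the daily schedule in step 3, with negatives set to 40, the days 10-12 figures rise from 27% v 40% to about 52% v 65%.

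**6. Continuous CT.** With negatives entered as 40 (assumed baseline mean 24, SD 4, daily tests), the tested-only difference between arms is 2.08 against 2.09 at days 4-6, and 1.27 against 1.41 at days 7-9, a loss of 0.14/1.41 = 10%. It is larger than the true difference later.

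**The case against.** The case against is substantial on several points.

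- **Clearance is compared elsewhere.** The prioritised analyses are a rank test with deaths ranked worst and Fisher's test of death or clearance beyond 10 days, with stratified versions. A Kaplan-Meier plot and individual PCR curves are also planned. None uses the window denominators, and the window tables carry no test. This stands and limits the point to descriptive tables.
- **The number missing will be shown.** True, so the shrinking base will be visible. But one count does not separate cleared, dead, discharged and untested patients, so a reader cannot recover the right denominator.
- **The kinetics objective concerns immediate viral load.** The 72-hour CT change is listed separately and is little affected, since few patients have cleared by then. This stands.
- **Stopping is permitted, not required, and optimal sites retest at Day 28-35 and Day 58.** True. The number tested after clearance is not given, so the size is illustrative.
- **Percent positive is named only for urine.** For blood the plan says qualitative, but its convention for categorical variables is number and percent.

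Two stronger readings are tempting. A reader might infer that the tables hide faster clearance on ZMapp. Only the ratio consistently moves toward 1; the point difference can grow. A reader might also infer that negatives fall out of the CT mean, which in one calculation cut the CT difference by about a quarter (1.4 instead of 1.8 at days 4-6; 0.9 instead of 1.2 at days 7-9). The plan does not say that a negative has no CT; it defines negatives by a CT cut-off and is silent on results reported without a number.

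**Conclusion.** The point holds for the level of positivity. The stopping rules and the denominator rule together make the blood-PCR windows from about day 7 overstate percent positive in both arms, and the averaging rule adds to it. At days 10-12 the illustrative size is 19-38% v 35-52% shown (ZMapp v oSOC), against about 9-12% v 22-29% of all survivors. The direction was the same under every clearance distribution and testing pattern tried. The size rests on assumed clearance times and test timing, anchored only by the pooled 13/49.

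The effect on the arm comparison is attenuation of the ratio and distortion of the point difference in either direction. The documents do not support a general claim that a ZMapp benefit is diluted, nor any effect on the primary outcome or the prioritised clearance analyses. The change is worth making because a by-arm table would otherwise be misread; it does not threaten the trial's conclusions.

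**What to change.** In Final DAP Section 3.9.1, for the qualitative blood-PCR windows:

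- use patients alive at the start of the window as the denominator;
- count a patient whose testing stopped after a negative as PCR-negative unless a later test is positive;
- classify status by the last result in the window, not by the averaged CT;
- show deaths, number tested and truly missing tests as separate rows;
- state that the Section 3 missing-data rule does not apply to tests omitted after clearance.

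For the continuous CT windows, state that a negative contributes CT 40, and show the number tested and the number already cleared beside each mean.

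The cost is DAP wording and a few lines of code, with no new data. One small downside is that a re-positive result after testing stopped would go unseen and be counted as negative, which matters somewhat in a trial that added follow-up for virologic relapse. The Day 28-35 and Day 58 retests at optimal sites partly cover this.
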